2.5 Quality Assurance

Due to COVID-19, research assistants will work remotely with pharmacies to complete the transitional pilot phase. Research staff will conduct a short online orientation with pharmacy staff participants to review the study activities. There are only two study activities for the transitional pilot phase: 1) place flyers in client participants' medication delivery packages about the study; 2) place posters about the study in their pharmacies and be willing to refer client participants with questions about the study to our research staff.

Research staff will proceed with the pilot phase of this study when in-person human interaction is favorable. Prior to the pilot phase, research assistants will undergo extensive training to ensure standardization of the pharmacy training protocol. Research staff will practice role-playing strategies to suggest various techniques for engaging client participants, which will be used during the pharmacy staff trainings.

To check the consistency of pharmacy PrEP delivery by pharmacy staff participants, the research staff will conduct at least one "test-buy" without knowledge to the pharmacy staff at each pharmacy. At enrollment and during informed consent, pharmacy staff participants will be made aware that we will be evaluating their services at various times throughout the data collection period and that our staff will not identify themselves as Emory research staff. If inconsistencies are observed, additional one-on-one trainings will be performed. Pharmacy activities will also be assessed through bi-weekly check-in visits/phone calls and through semi-structured interviews. This will help inform potential changes and/or booster trainings that may need to take place. While pharmacy staff participants will have gone through extensive training on how to engage their client participants, our research staff will closely monitor the first couple of months to encourage the highest quality of service delivery.

2.6 Risks to participation

In terms of the key stakeholder surveys and workflow assessments completed for Aim 1, there are no psychological, social or biological risks involved.

In the transitional pilot phase, research assistants will engage with pharmacy staff participants online through Zoom. Pharmacy staff participants will complete a short orientation of the study activities. Pharmacy staff participants will also earn 2 CE credit through an online training seminar to learn how to mobilize pharmacies to improve PrEP access. There are only two study activities for this phase. Firstly, pharmacy staff participants will place flyers within their client participants' medication delivery packages. Secondly, pharmacy staff participants will hang posters about the study and the assessments in their pharmacies.

With COVID-19 unabated, pharmacies primarily deliver medication to their client participants, which provide the opportunity to place study flyers in client participants' medication delivery packages. Additionally, few pharmacy client participants still visit pharmacies. Pharmacy staff participants will place posters in their pharmacies to increase customer engagements with the study information. The aforementioned study activities do not require pharmacy staff participants to perform duties outside of their current scope of practices. Therefore, there are no additional psychological, social or biological risks involved. However, there are minimal risks for pharmacy client participants who complete the eligibility and social and behavioral screeners to determine behavioral eligibility for PrEP. Pharmacy client participants may feel mild discomfort in answering personal and lifestyles questions.

In the pilot study phase, pharmacy staff participants will inform pharmacy clients about the study and will be trained on the importance of confidentiality and discretion with respect to the pharmacy client participants. Pharmacists have extensive experience working with patients for a host of health outcomes and are bounded by the Code of Ethics that are adopted by the American Pharmacists Association. The Code of Ethics promote covenantal relationship, respect, and confidentiality for every patient. Therefore, we do not foresee any problems with pharmacists' ability to uphold fundamental principles of ethics when interacting with study participants⁴⁸.

We will, however, provide additional training to pharmacy staff participants on research ethics during the pharmacy training. There is a small possibility of other patrons in the pharmacy over-hearing pharmacy staff discuss the study with potentially eligible pharmacy client participants. To circumvent this, we will train pharmacy staff participants to engage pharmacy client participants during a discreet time when customer flow is low. Discussions of sensitive topics (i.e., drug and sex behaviors, PrEP, HIV, etc...) will be conducted in a private room or an area that we have created with partitions, noise cancelling curtains and a sound machine to muffle noise.

There are minimal risks for pharmacy client participants who complete the social and behavioral screener to determine behavioral eligibility for PrEP. For those who are behaviorally appropriate for PrEP and agree to be clinically screened for PrEP (HIV testing), they may learn that they have a positive HIV diagnosis, which may result in emotional or psychological distress. The pharmacy staff participant, who will undergo intensive post-test counseling training, will counsel the patient. The pharmacy staff participant will immediately link the patient to confirmatory testing and HIV care through our community partners at NAESM (who have significant experience counseling and treating newly diagnosed patients) or co-I [name] who directs Atlanta's Fulton County HIV clinic. We will provide transportation for those who test HIV positive to the clinic and research assistants from Emory and

NAESM will be available to accompany the patient if needed. NAESM and [name] have extensive experience working directly with patients who have HIV. They will be available to study participants who need referrals, are not linked to a regular health care provider and need health care treatment. We will also provide mental health referrals tailored to their needs and community.

2.7 Adequacy of Protection Against Risks

Recruitment and Informed Consent

For the key stakeholder interviews and workflow assessments (Aim 1), written informed consent will be obtained at recruitment into the study. The data will be summarized within each key stakeholder subgroup without the inclusion of personal identifying information.

For the transitional pilot phase, pharmacy staff participants will provide written informed consent once the pharmacy is recruited into the study. We will complete pre/post pharmacy training surveys as well as baseline and 3-month surveys throughout the period of the transitional study. These data will include personal identifying information as this will be used for tracking quality control and identifying areas where the pharmacy PrEP delivery model needs adjustment for the pilot phase.

Also, in the transitional pilot study, pharmacy client participants will provide electronic informed consent before initiating the eligibility screener and social and behavioral survey. Participants will receive links and given instructions to take surveys. The screener and survey will provide a brief statement regarding the purpose of the study. Pharmacy client participants who take the eligibility screener will be compensated a \$1 pharmacy coupon. Pharmacy client participants who are eligible and take the social and behavioral survey will be compensated \$25 for their time. Before survey questions appear, pharmacy client participants will provide electronic consent, similar to online surveys. On the consent, pharmacy client participants are told that they may refuse to answer any question or to drop out of the study at any time they feel uncomfortable with the process. This wording will be bolded. Surveys will be administered privately through the use of Alchemer; we will have the participant select their answers using their mobile or other electronic devices. Alchemer can be used on mini-computers, tablets, and phones (which increases privacy). They will be told that the information obtained will be summarized with information from others and only aggregate data will be reported; that in no case will individual information be released (except to the pharmacy who is liable under Health Insurance Portability and Accountability Act of 1996) without their written consent. Records of the consent, which include personal identifying information will be stored in locked files separate from data collection forms that have no personal identifying information but are noted with a unique study number.

For the pilot study, pharmacy staff participants will provide written informed consent once the pharmacy is recruited into the study. We will complete pre/post pharmacy training surveys as well as baseline, 3-month and 6-month surveys throughout the period of the pilot study. Pharmacy staff participants will also complete electronic logs of their recruitment efforts of the study population. These data will include personal identifying information as this will be used for tracking quality control and identifying areas where the pharmacy PrEP delivery model needs adjustment.

Also, in the pilot study, pharmacy client participants will provide electronic informed consent before initiating the social and behavioral screening survey. For pharmacy client participants who are interested in being in the study, pharmacy staff participants will escort the pharmacy client participant to a private

area where they can begin the electronic informed consent process. On the consent, pharmacy client participants are told that they may refuse to answer any question or to drop out of the study at any time they feel uncomfortable with the process. This wording will be bolded. Surveys will be administered privately through the use of Alchemer we will have the participant listen to questions via headphones and mark their answers using the touch screen tablet computer. Alchemer can be used on mini-computers and tablets (which increases privacy). They will be told that the information obtained will be summarized with information from others and only aggregate data will be reported; that in no case will individual information be released (except to the pharmacy who is liable under Health Insurance Portability and Accountability Act of 1996) without their written consent. Under Georgia State law, the researcher(s) will not maintain as confidential, information about known or reasonably suspected incidents of abuse or neglect of a child, elder, or vulnerable adult, including but not limited to physical, sexual, emotional, and financial abuse or neglect. If any researcher has or is given such information, he or she may be required to report it to the authorities. Records of the consent, which include personal identifying information will be stored in locked files separate from data collection forms that have no personal identifying information but are noted with a unique study number. Those records will be stored in a physically secure environment. All data files will have encryption and strong password protection. Any identifiable data will be stored on Emory University's secure servers.

Protections Against Risk

In terms of the key stakeholder surveys and the pharmacist/ technician surveys during the transitional pilot phase and pilot phase of the study, there are no psychological, social or biological risks involved.

Since in this proposed research plan, pharmacy client participants will be informed about the study by the pharmacy staff participants, the importance of confidentiality will be conveyed to all study pharmacy staff participants. To minimize the risk of pharmacy client participants feeling uncomfortable about answering personal questions, we will use an electronic survey platform, Alchemer, for the study's surveys. In Alchemer, participants will select answers to the survey questions. In the Alchemer survey, participants listen to questions via headphones and mark their answers using the touch screen tablet computer. During the transitional pilot phase, pharmacy client participants will self-interview using Alchemer. However, for the pilot phase, pharmacy staff will be available to assist participants with questions regarding technical difficulties on Alchemer. But, for questions specific to the pharmacy client participants data or survey instrument, the participant will be told that they can call or videoconference an Emory research assistant. Pharmacy client participants may refuse to answer any question that makes them uncomfortable.

To minimize risks to confidentiality, we will secure study data with all appropriate physical, electronic and operational protections. Data will be stored in a physically secure environment. All data files will have encryption and strong password protection. Any identifiable data will either be stored on Emory University's secure servers or will be on fully encrypted laptops. Alchemer surveys will take place on an encrypted commercial survey website, SurveyGizmo (<http://www.surveygizmo.com/survey-software-features/secure-link/>). This site has been used by one of our Co-I for thousands of online surveys with MSM with no data security breaches. Access to data will be on a role-based standard; only those study staff who require access to each type of data to complete their study- related roles will be allowed access. All study staff will be trained in security and confidentiality procedures and will sign a confidentiality agreement before receiving access to any participant data. While we do not expect any problems, all adverse events and unanticipated problems will be promptly reported to the Emory IRB.

2.8 Reportable events

All adverse events and unanticipated problems will be promptly reported to the Emory IRB and/or NIH program official in accordance with the NIMH reportable events policy for definitions and timeframes.

2.9 Benefits to subject or future benefits

Although there are no direct personal benefits to the participants included in the study, the results of the study will lay the critical groundwork for understanding whether pharmacy PrEP delivery can be achieved for BMSM in high poverty, racial minority neighborhoods. This study will inform a future efficacy trial that is implemented to test the uptake of PrEP through pharmacies for BMSM. In addition, this model could be adopted for pharmacies across the country, in communities at high risk for HIV, and other underserved populations in the US without another point of access to PrEP in their communities.

2.10 Compensation

Formative Phase

Pharmacists, technicians, PrEP-prescribing physicians, and BMSM will be compensated \$50 for 1.5 hours for their time completing the interview. Pharmacists and/or PrEP-prescribing physicians will receive an additional \$50 for their time if we perform a guided walk around of their office to assess their workflow.

Transitional Pilot Phase

During the transitional pilot phase, each pharmacist participant will receive \$250 for 3 months of participation in study activities as outlined in the pharmacist participant consent forms. Each pharmacy staff participant (we estimate 1 pharmacist and 3 technicians per pharmacy) will receive \$25 for the orientation session plus \$25 for each semi- structured interview. We have noted that this amount of compensation for pharmacy staff has been sufficient in earlier work with pharmacies. Pharmacy client participants who agree to complete the eligibility screener and social and behavioral survey will be compensated \$1 and \$25, respectively, for their time regardless of their eligibility or

interest in being clinically screened for PrEP.

Pilot Phase

In this proposed study, each pharmacist participant will receive \$2,500 (\$1,250 for each pharmacist participant in the pharmacy) for 6-months of participation in study activities as outlined in the pharmacist participant consent forms. Each pharmacy technician participant (we estimate 3 technicians per pharmacy) will receive \$50 for the training session plus \$25 for each semi-structured interview. We have noted that this amount of compensation for pharmacy technician participants has been sufficient in earlier work with pharmacies. Additionally, pharmacies will be compensated for the price of PrEP medication and be provided with a dispensing fee of \$50 per bottle.

Pharmacy client participants who agree to complete the social and behavioral screener will be compensated \$25 for their time regardless of their eligibility or interest in taking an HIV test.

2.11 Data analysis

Formative Phase

Qualitative interviews will be taped and transcribed. Field notes from the workflow assessment will be transferred to electronic files. Two separate interviewers will double code the transcripts and workflow assessments for content and themes in order to identify emergent patterns⁴⁹. As the domains are defined, we will construct a preliminary codebook, and coding scheme. Transcripts will be coded into Atlas.ti with open codes first in order to identify broad themes or patterns. Following open coding and broad thematic analysis, transcripts will be coded with axial codes, or more interpretive codes that will be used in order to identify core concepts. With coherent axial coding we will construct detailed narratives of the interviewees understanding of the pharmacy PrEP delivery model and how it can be implemented in the context of their current day-to-day activities.

Intervention Development Phase

The advisory board will provide feedback on the study protocol, pharmacy trainings, pharmacy recruitment brochure, survey instruments and other materials as needed. We will also iteratively revise the protocol over the course of the study to ensure its feasibility, acceptability, and safety. Adaptive protocol development is recommended in early phase clinical trials since it allows for continued process improvement and time-savings from data as it is being collected^{45,46}. We will debrief about the study activities **every month** of the pilot study to refine the protocol for immediate implementation in the study activities. Each proposed change will be assigned a subject matter expert from the co-I's on the grant. The subject matter expert and at least two other co-I's will be asked to vote on whether the change will be made immediately, revoked or followed through the next monthly meeting. Meticulous records of the development and revision process of the pharmacy PrEP delivery model will be kept throughout the study.

Transitional Pilot Phase

Quantitative data will be transferred to analyses using analysis software (i.e., SAS) to derive descriptive statistics and quantitative profiles of customer data. Exploratory data analysis (EDA) will be conducted through data editing using SAS. EDA will include calculation of means, medians, percentages,

proportions, standard deviations, and skewness/kurtosis as appropriate. If outliers or nonstandard distributions exist, variable transformations or standardized cut-points in the data will guide recoding of continuous variables. Externally validated standards will be used to recode the data if possible. The influence of outliers will be assessed and medians (or rank tests) used if required. Differences between two means (or medians) will be tested using t- tests or rank tests and categorical variables will be compared between groups using Chi-square tests, exact tests and/or with 95% confidence intervals to guide interpretation. Correlates of interest include health insurance, sexual behavior, substance use and HIV testing behavior. Other relevant mediators and/ or confounders will include variables such as previous and/ or consistent access to health care. We plan to separately examine the relationship between each confounder and outcome of interest using t-tests or rank tests on continuous measures and exact tests on categorized values if categorizations are used. Initial unadjusted comparisons will be made using exact tests. If significant bivariate associations are found, we will incorporate these exposures as covariates using linear regression for continuous variables and logistic regression for binary variables where sample size allows.

Pilot Phase

Pharmacist and technician participant data

Transcripts from the audio-recorded pharmacists and technician interviews will be loaded into Atlas.ti, a qualitative data analysis software package. Research assistants will enter the data immediately so that intervention activities and protocols can be altered during the study, if needed. Patterns of knowledge, beliefs, behaviors, and practices that point to practical barriers or facilitators of effective training of pharmacists, feasibility of intervention delivery and effective risk reduction will be identified. These data will include pharmacy-identifying information so that each pharmacy can be monitored for consistency of study activities. In terms of quality control, these data will also be used to inform the necessity of additional training for pharmacy staff.

For the data analysis, all interviews will be double coded by two different research assistants. Topic guides for the interviews will be used to establish preliminary codes for interpretation. Coding will begin with the first interview by creating open codes of broad themes found in the four SEIPS components of inquiry: person, organization, environment and tasks. More interpretive codes within those open codes will then be used to identify patterns of knowledge, beliefs, behaviors, and practices that point to practical barriers or facilitators of effective training of pharmacists, feasibility of intervention delivery and effective pharmacy PrEP delivery.

Pharmacy client participant data

Formation of new variables and collapsing variables will be done when exploring the proportion and correlates of feasibility, acceptance, safety and PrEP use at baseline and at 3-months among BMSM. Exploratory data analysis (EDA) will be conducted through data editing using SAS. EDA will include calculation of means, medians, percentages, proportions, standard deviations, and skewness/kurtosis as appropriate. If outliers or nonstandard distributions exist, variable transformations or standardized cut-points in the data will guide recoding of continuous variables. Externally validated standards will be used to recode the data if possible. The influence of outliers will be assessed, and medians (or rank tests) used if required. Differences between two means (or medians) will be tested using t- tests or rank tests and categorical variables will be compared between groups using Chi-

square tests, exact tests and/or with 95% confidence intervals to guide interpretation. Correlates of interest include health insurance, sexual behavior, substance use and HIV testing behavior. Other relevant mediators and/ or confounders will include variables such as previous and/ or consistent access to health care. We plan to separately examine the relationship between each confounder and outcome of interest using t-tests or rank tests on continuous measures and exact tests on categorized values if categorizations are used. Initial unadjusted comparisons will be made using exact tests. If significant bivariate associations are found, we will incorporate these exposures as covariates using linear regression for continuous variables and logistic regression for binary variables where sample size allows.

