Aim 1. Develop a pharmacy PrEP delivery model by evaluating the barriers to and facilitators of integrating PrEP into existing pharmacy practice among key stakeholders (pharmacists, technicians, PrEP-prescribing physicians and BMSM).

Aim 2. Evaluate eligibility and willingness to receive PrEP in pharmacies among BMSM and collect data on customer engagement with PrEP delivery information from pharmacy staff during COVID-19.

Aim 3. Pilot test the pharmacy PrEP delivery model and examine its feasibility, acceptability and safety, and gather early evidence of its impact and cost with respect to PrEP uptake at baseline and at 3-months (the clinically suggested follow-up period) among pharmacy client participants.

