2. Pharmacy staff participants will provide a pharmacy brochure highlighting that they offer pharmacy PrEP delivery tailored to the Atlanta area and for those who patronize the pharmacy. Pharmacy posters normalizing PrEP and HIV will be carefully tailored to the community of the pharmacy. These posters will be designed to appeal to the general customer base and be placed inside and outside of the pharmacy. These posters will be placed with other health literature to avoid singling out HIV-related services that may inadvertently add stigma.
3. Pharmacy staff participants will discreetly inform pharmacy clients (n=60) about the study. Pharmacy clients who are interest and willing will complete an electronic eligibility screener.
 - a. *In cases of long lines in the pharmacy and privacy is not possible, we will discourage pharmacy staff from delivering detailed information (at this particular visit) to protect anonymity of their customer; this will be done consistently across each pharmacy.*
4. Pharmacy client participants who agree to participate will be directed to an area where they can privately provide electronic informed consent and complete the eligibility screener. They will be informed at the end of the survey if they are eligible for the 20-minute social and behavioral survey via an electronic prompt. Eligible pharmacy client participants can immediately complete the social and behavioral survey or return to the pharmacy at a later time to do so. and their customer visit will be logged.
5. The consent form and survey will be self-administered via an electronic tablet so it will NOT require the presence of the pharmacy staff participants outside of them directing them to the private room where the tablet is set up. To circumvent potential literacy issues, the participant will listen to questions via headphones and mark their answers using the touch screen computer. If the participant has a physical or mental condition that renders them unable to use the tablet, the survey will be administered orally by a study team member. Audio recordings of the questions will be utilized throughout Alchamer wherever possible in case of literacy barriers.

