 - a. They will be assured that we will only use this information to follow-up with them about the study and their information nor personal data will be shared with anyone other than themselves.
9. The pharmacy staff participants will process/ interpret the results of the rapid HIV test first in case a treatment referral needs to be set up.
10. Pharmacy client participants who test HIV negative will be provided with their results and be given a 30-day prescription for PrEP, culturally appropriate PrEP counseling and a follow-up appointment with co-I [name] or another PrEP prescribing physician identified through PrEPlocator.org, whichever is closest.
 - a. A PrEP prescribing physician will be available via phone during the testing process to provide participants with a prescription of 30-day PrEP.
 - b. We will inform the individual that a 30-day PrEP prescription will be required to achieve protection from HIV but in order to sustain protection, they need to continue PrEP beyond the 30-day period.
11. Pharmacy client participants may refuse to participate at any time or if they have time constraints, they can schedule the clinical screening at a later date. If they are uncomfortable completing the screening in the pharmacy, we will also provide them with a referral for a PrEP prescribing physician.
12. Pharmacy client participants who test HIV positive will receive post-test counseling from the pharmacy staff, who underwent intensive post-test counseling. Pharmacy client participants will be immediately sent for confirmatory testing and linkage to treatment at our community partner (NAESM) or co-I [name].
 - a. If needed, we will provide transportation for those who test positive to the clinic (if physically open pending COVID-19) and a research assistant from Emory or NAESM will be available to accompany the participant.
13. Pharmacy client participants who have an inconclusive HIV test will be told that their test is inconclusive and will be referred to our community partner, NAESM, for a confirmatory HIV test.
14. Once the pharmacy client participant completes the study activities they will be thanked for their time. In case of inclement weather, a research team member will offer to order an Uber or Lyft for the participants.

15. We will complete a 3-month follow-up phone call with pharmacy client participants who have test for HIV to assess linkages to PrEP/HIV care.

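### The pilot's regression covariates are picked by a significant bivariate test; with 60 clients at best, modest adjusted odds ratios would tend to come out too large (minor, cheap to fix).

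*Combined protocol and SAP*

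**What the plan says.** Section 2.11 (Pilot Phase, Pharmacy client participant data) describes the client analysis as "exploring the proportion and correlates of feasibility, acceptance, safety and PrEP use at baseline and at 3-months among BMSM". It names four correlates (health insurance, sexual behavior, substance use, HIV testing behavior) and adds an open list: "Other relevant mediators and/ or confounders will include variables such as previous and/ or consistent access to health care". Screening is one variable at a time: "We plan to separately examine the relationship between each confounder and outcome of interest using t-tests or rank tests on continuous measures", with exact tests for categorized values. The rule for model entry follows: "If significant bivariate associations are found, we will incorporate these exposures as covariates using linear regression for continuous variables and logistic regression", subject to a qualifier that the sample size must permit it. The section gives no significance level, adjustment set or maximum number of covariates, and does not say which listed variables are mediators.

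The Transitional Pilot Phase part of 2.11 has the same rule: "If significant bivariate associations are found, we will incorporate these exposures as covariates using linear regression". No client number is stated for that phase.

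For the pilot, 2.4 (Pharmacy-based PrEP delivery) gives one number: "Pharmacy staff participants will discreetly inform pharmacy clients (n=60) about the study". At 3 months the contact is narrower: "We will complete a 3-month follow-up phone call with pharmacy client participants who have test for HIV to assess linkages to PrEP/HIV care". Aim 3 in 1.1 wants the pilot to "gather early evidence of its impact and cost with respect to PrEP uptake at baseline and at 3-months", and 2.9 says the study will inform a later efficacy trial.

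**The concern.** In a small sample a test is significant only when the observed association is large. If significance is the ticket into the model, the adjusted estimates that appear are those that happened to be large. For a modest true effect, most samples give no adjusted estimate, and the rest give one that is too high. A reader who sees an adjusted odds ratio of 4 for PrEP use has no sign that the truth may be nearer 2.

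The analysed number is 60 at best. It is probably smaller at 3 months, since only clients tested for HIV are called, and smaller again if the analysis is confined to BMSM. At stake is which correlates of PrEP use are stressed when the pilot is used to inform the next trial. A second, smaller gap is that mediators and confounders are listed together, so a variable such as access to care could be adjusted for where it lies on the pathway.

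**Working it through.** The plan states no power, effect size or alpha for these models, so there is no figure of its own to reproduce.

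**Inputs.** From the documents: n of at most 60 (2.4), exact screening tests and entry by significance (2.11). Assumed: two-sided alpha 0.05 (in line with the 95% intervals in 2.11), binary variables, 40% exposed, 40% with the outcome, and the true odds ratios (OR) shown. An n of 45 at 3 months is also assumed.

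**1. Smallest OR that can pass.** With 40% exposed, 60 clients split 24/36. Over all tables with that split, the smallest OR above 1 with Fisher p<0.05 is at 15/24 versus 12/36: OR = (15×24)/(9×12) = 3.33, p = 0.035. At n=45 (18/27) it is 12/18 versus 9/27: OR = (12×18)/(6×9) = 4.0, p = 0.037.

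**2. Single screen.** The group rates solve 0.4·p1 + 0.6·p0 = 0.40 with [p1/(1−p1)]/[p0/(1−p0)] equal to the true OR. For OR 2 this gives p0 = 1/3 and p1 = 1/2. Exact enumeration at n=60:

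| True OR | Passes | Median OR when it passes |
|---|---|---|
| 2 | 19.7% | 4.20 |
| 3 | 45.5% | 4.90 |
| 4 | 65.8% | 5.25 |
| 5 | 79.0% | 6.00 |

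With outcome rates of 20-60% and exposure rates of 30-50%, a true OR of 2 passes in 11-20% of runs, with median 4.1 to 7.0.

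**3. Adjusted model.** Simulation at n=60: five binary candidates at 40%, latent correlation 0.2, two real and three null. Gated means Fisher p<0.05, then a logistic model of those passing. Fixed means three covariates (both real, one null).

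| True OR | Gated median | Fixed, every run | Fixed, read only if p<0.05 |
|---|---|---|---|
| 2 | 4.1 | 2.1 | 4.3 to 4.4 |
| 3 | 4.7 | 3.2 | 5.1 |
| 4 | 5.4 | 4.4 | 6.1 |
| 5 | 6.3 | 5.6 | 7.0 |

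Ratio to truth, gated: 4.1/2 = 2.1, 4.7/3 = 1.6, 5.4/4 = 1.4, 6.3/5 = 1.3. At OR 2 nothing enters in 54% of runs. When a real covariate does enter, its 95% interval covers the truth 89% of the time (95% with the fixed set). At OR 3 or more, coverage is not harmed. At n=45 and true OR 2 the gated median is 5.1, against 2.1 fixed.

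**4. Larger samples.** At true OR 2 the gated median falls to about 2.4 at n=150 and 2.1 at n=300.

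**5. Confounder lost at the screen.** A confounder with outcome 55% versus 30% fails the screen in 58-60% of runs at n=60. The average bias in the log-OR of a null exposure is +0.10 (unadjusted +0.28, fixed −0.01), against a standard error of about 0.59.

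**6. Precision after the change.** Unadjusted, OR 2, n=60: SE = √[1/(24×0.5×0.5) + 1/(36×⅓×⅔)] = √(0.167 + 0.125) = 0.54, so the 95% interval is 2×exp(±1.96×0.54), about 0.7 to 5.8. In the three-covariate model the median interval is about 0.7 to 6.7.

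**The case against.** The strongest objection is that step 3 compares unlike things: gated estimates exist only after passing a test, while the fixed-model figure averages every run. Read the fixed model only when p<0.05 and it exaggerates as much or slightly more. This stands. Fixing the covariates does not cure the problem alone; the gain comes from removing the gate and reporting every estimate.

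The work is also labelled exploratory, the correlates are partly named in advance, and 95% intervals are mentioned. All true, but entry to the model is still data-driven. The sample-size qualifier may limit how many covariates enter, not how they are chosen. It is still a sensible safeguard: at an assumed 10% outcome rate (60×0.10 = 6 outcomes) a three-covariate fit separated or failed to converge in 23% of runs at n=60 and 39% at n=45. At 20% the figures were 2% and 5%.

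A reader might infer more than the documents support:
- *That non-significant results will be withheld.* The rule governs model entry; nothing in 2.11 says bivariate results will go unreported.
- *That gated odds ratios will size or shape the efficacy trial.* Section 2.9 says only that the study will inform it.
- *That the transitional phase is materially harmed.* No client number is given there, and step 4 shows the effect would be small in a larger sample.
- *That dropped confounders badly bias the results.* Step 5 shows a small average bias.

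**Conclusion.** Minor, and worth fixing because the change is cheap. The rule is plainly stated, and at 60 clients or fewer it would about double the adjusted odds ratio for a true value near 2 whenever that variable enters a model, with less exaggeration for larger effects. The direction held in every setting tried. The exact size rests on assumed alpha, outcome and exposure rates, correlation and true odds ratios, none of which the documents supply, so exaggeration is the expected behaviour of the rule and not a demonstrated result. The harm is confined to the exploratory adjusted models and to any emphasis placed on them. It does not reach the feasibility, acceptability, safety or uptake proportions, and the pilot has no randomised treatment effect to bias.

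**What to change.** In 2.11, Pharmacy client participant data:

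1. Delete the sentence that makes model entry depend on a significant bivariate test.
2. Report the unadjusted estimate with a 95% interval for every named correlate, whatever its p-value.
3. Where the number of outcomes allows, fit a short covariate set (two or three, for example) chosen beforehand on subject-matter grounds, and report all its estimates with 95% intervals. If outcomes are sparse, use a penalised (Firth) fit or give unadjusted estimates only.
4. For each correlate-outcome pair, decide in advance whether access to care is a confounder or a mediator, and do not adjust for it where it is a mediator. The decision belongs to the pair, since a mediator for one correlate may be a confounder for another.

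Use the same wording in the Transitional Pilot Phase part of 2.11, for consistency only.

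The cost is a text change with no new data. The downside is wide intervals (step 6) and fewer significant correlates to report, which fairly reflects what 60 clients can show.
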